7.2. Setting

7.2.1. Inclusion criteria

To be included in the study all patients will have received at least 1 dose of Xeljanz for the treatment of the following indication as per local labelling:

- Moderately to severely active ulcerative colitis (UC) who have had an inadequate response or intolerance to the basic treatments or biological agents

7.2.2. Exclusion criteria

Patients meeting any of the following criteria as per the local labeling will not be included in the study:

1. Patients with a history of hypersensitivity to any ingredients of this product.
2. Patients with serious infection (sepsis, etc.) or active infection including localized infection.
3. Patients with active tuberculosis.
4. Patients with severe hepatic function disorder.
5. Patients with an absolute neutrophil count (ANC) <1,000 cells/mm³.
6. Patients with a lymphocyte count <500 cells/mm³.
7. Patients with a hemoglobin level <9 g/dL.
8. Pregnant or possibly pregnant women.
9. Because of lactose contained in this drug, it should not be administered to patients with hereditary problems of galactose intolerance, Lapp lactase deficiency or glucose-galactose malabsorption.

7.2.3. Duration of the study

According to the MFDS re-examination regulation, the analyzed study report based on 4 years of collected data has to be submitted to MFDS within 3 months after the end of specified re-examination period (from the indication approval date to 4 years afterwards). The re-examination period is from 20 September 2018 to 19 September 2022, and the final study report should therefore be submitted by 19 December 2022.

CCI [REDACTED]

[REDACTED]

[REDACTED]

CCI [REDACTED]

[REDACTED]

CCI

CCI

CCI

CCI

CCI

CCI

CC1

CCI

CCI

CC1

7.2.5. Study procedures

Patients will be enrolled by continuous registration method. The investigator should enroll all patients to whom Xeljanz is prescribed for the first time according to the local product label and who agree to participate in this study by signing the data privacy statement (used in place of the informed consent form). Xeljanz will be medicated by the investigator's prescription under usual clinical practice. Pfizer Korea will not provide the medicinal product for this study.

There will be no mandatory visit during the study. The investigators will collect relevant data from the time of initiating administration of Xeljanz until 24 weeks of treatment (52 weeks of treatment for the long-term users). If the patient does not complete 24 or 52 weeks of treatment, relevant data should be collected based on the last assessment performed at the time of treatment discontinuation. The investigator should record the following information on the patient's CRF.

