7.3.1.2. Laboratory test

Recommended laboratory tests and time points are included in Table 4. Test results of chest X-ray, erythrocyte sedimentation rate (ESR), C-reactive protein (CRP), other blood chemistry, hematology, and tuberculin test should be recorded, if conducted.

Table 4 Recommended Laboratory Test

	Lymphocyte	Neutrophils	Hemoglobin	Lipids (TC, HDL, LDL)
Baseline	X	X	X	X
4 to 8 weeks after treatment		X	X	X
Every 3 months	X	X	X	

Abbreviations: TC=total cholesterol, HDL= high density lipoprotein, LDL=low density lipoprotein.

In case there are any clinically significant laboratory abnormalities (as per the investigator's judgment) that occur after the treatment of Xeljanz compared to baseline, the tests should be recorded in detail on the CRF, including test results before and after Xeljanz treatment, a causal relationship to Xeljanz, and any comments from the investigator.

Please refer to [Section 9.4.1](#) for the criteria for determining whether an abnormal objective test finding should be reported as an AE.

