7.3.2. Effectiveness variables

The Mayo score or the Partial Mayo score at week 8, 16, 24 and also 52 for the long-term users is assessed to see the remission, clinical response or mucosal healing. Investigator will perform the final effectiveness evaluation of the drug into 4 categories based on the clinical impression plus Mayo score or Partial Mayo score ('Improved', 'Unchanged', 'Aggravated', 'Not assessable').

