### 3.2. Efficacy Analysis Set

The Efficacy analysis set will be included all patients entering this study for the safety analysis whose efficacy data are available after 24 weeks of treatment, or based on the last assessment performed at the time of treatment discontinuation if the patient does not complete the 24 weeks of treatment. If the patient does not complete the 24 weeks of treatment, the cause of discontinuation will be assessed.

The cases below shall be excluded from the efficacy analysis set in the following order:

- 1) Subjects who are excluded from the safety analysis set
- 2) Subjects without general efficacy assessment by the investigator
- 3) Subjects who are evaluated general efficacy assessment as 'Not assessable' by the investigator
- 4) Subjects who are have been administrated Xeljanz® for less than 8 weeks (56 days)

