### **5.2. Handling of Missing and Incomplete Data**

#### **5.2.1. Handling of Missing Data**

If data are missing or if a subject decided to discontinue from the study, there will be no imputation applied except as specified in section 5.2.2. The impact of missing data will be evaluated as appropriate.

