### 6.3. Efficacy Analyses

Efficacy analyses will be performed based on data of efficacy analysis set

- 1) Mayo index, Mayo score and partial Mayo score
  - Mayo index (stool frequency, rectal bleeding, physician's global assessment and finding of endoscopy), Mayo score or partial Mayo score at baseline, week 8 ( $\pm 15$  days), week 16 ( $\pm 15$  days), week 24 ( $\pm 15$  days) and changes from the baseline to last value will be presented in n, mean, SD, median, minimum and maximum. And changes from the baseline to last values will be tested by using paired t-test (or Wilcoxon signed rank test).
- 2) Mucosal healing (If endoscopy was done)
  - Mucosal healing at week 8 ( $\pm 15$  days), week 16 ( $\pm 15$  days), week 24 ( $\pm 15$  days) will be presented in frequency and percentage.
    - Achieved
    - Not achieved
- 3) Remission
  - Remission at week 8 ( $\pm 15$  days), week 16 ( $\pm 15$  days), week 24 ( $\pm 15$  days) will be

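### The ±15-day windows in SAP 6.3 leave days 72–96 and 128–152 unassigned, and remission, response and mucosal healing have no last-assessment table to catch those scores

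*Protocol*

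**What the plan says.** Protocol 7.2.5 leaves visit timing to usual practice: "There will be no mandatory visit during the study". Protocol 7.3.2 still names target weeks: "The Mayo score or the Partial Mayo score at week 8, 16, 24 and also 52 for the long-term users is assessed". Section 7.3.3 repeats weeks 8, 16 and 24 for the investigator's evaluation.

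SAP 6.3 attaches a window of 15 days either side to each of these weeks. It applies to the Mayo components and scores, to remission and clinical response, and to healing ("Mucosal healing at week 8" and the later weeks). Two analyses in the same section carry no window:

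- the Mayo change, where "changes from the baseline to last values will be tested by using paired t-test (or Wilcoxon signed rank test";
- the investigator's final assessment, with the subgroup and regression analyses of the effective rate.

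On missing data, SAP 5.2.1 says "there will be no imputation applied except as specified in section 5.2.2", and that the impact of missing data will be evaluated as appropriate. I found no rule for a score outside every window, and none for choosing between two scores inside one window.

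For patients who stop early, SAP 3.2 and 4.2 (and Protocol 7.2.5, 7.3.3 and 7.7.2) rely on the last assessment made at discontinuation. SAP 3.2 excludes from the efficacy set those treated "for less than 8 weeks (56 days").

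**The concern.** Gaps between windows do little harm when visits are scheduled at the targets. Here attendance follows routine care, so some scores can be expected between windows. Those scores have been collected and are valid, yet three of the time-point outcomes have no place for them.

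The patients who stop treatment matter most. The plan says their last assessment should be used, but for remission, response and healing SAP 6.3 offers only the windowed weeks. If patients stopping for lack of effectiveness have closing scores between windows, the reported rates describe a group that has lost some of its failures.

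**Working it through.** **Inputs**

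- Target weeks 8, 16 and 24: Protocol 7.3.2.
- Half-width of 15 days: SAP 6.3.
- Conversion of 8 weeks to 56 days: SAP 3.2.

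The plan gives no figure of its own to reproduce.

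**Windows**, as 7 × week ± 15, with first dose as day 0:

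| Target | Day | Window | Length |
|---|---|---|---|
| Week 8 | 56 | 41–71 | 31 |
| Week 16 | 112 | 97–127 | 31 |
| Week 24 | 168 | 153–183 | 31 |

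**Gaps**

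- Days 72–96: 96 − 72 + 1 = 25 days.
- Days 128–152: 152 − 128 + 1 = 25 days.
- Span of days 41–183: 183 − 41 + 1 = 143 days.
- Covered: 3 × 31 = 93. Uncovered: 143 − 93 = 50, and 50/143 = 35%.

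Counting first dose as day 1 moves the gaps to days 73–97 and 129–153. Their length is unchanged.

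**Share of scores outside a window.** The documents give no distribution of visit days, so this is an assumed range. For visit days normally distributed around each target, the share outside is 2 × [1 − Φ(15/SD)]:

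| Assumption | Share outside |
|---|---|
| SD 7 days (15/7 = 2.14) | about 3% |
| SD 10 days (15/10 = 1.50) | about 13% |
| SD 14 days (15/14 = 1.07) | about 28% |
| Even spread over days 41–183 | 35% |

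These are shares of scores, not of patients. A patient scored at intervals of 31 days or less has a score in every window while under follow-up, and loses no time point to a gap.

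**Where a gap score can go**

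| SAP 6.3 analysis | Windowed only? | Can a gap score enter? |
|---|---|---|
| Mayo components and scores by week | Yes | No |
| Change from baseline to last value | No | Yes, if it is the last |
| Mucosal healing | Yes | No |
| Remission | Yes | No |
| Clinical response | Yes | No |
| Investigator's final assessment | No | Yes, as information to the investigator |

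**A patient who stops early.** Suppose treatment stops, and the last score is taken, on day 80 or day 140. Both exceed 56 days, so the treatment-duration exclusion does not apply and the patient can be in the efficacy set. Day 80 lies in 72–96 and day 140 in 128–152. The closing score therefore enters none of the remission, response or healing tables. An earlier score inside a window would still be shown, so a patient who responded by week 8 and then failed would appear only as a responder.

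**The case against.** The best defence is that the protocol does name weeks 8, 16 and 24, so investigators will tend to record scores near them, and 31 days is a reasonable allowance. Fixed narrow windows are a recognised choice and keep the weekly labels honest. Safety is the primary endpoint. The only Mayo analysis that is tested, and the investigator's evaluation that Protocol 7.1 presents as the secondary endpoint, are both free of windows. The SAP also never says in words that out-of-window scores are dropped.

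Much of this stands. It limits the size of the problem and confines it to descriptive tables. It does not supply an assignment rule, and it does not give remission, response or healing a last-assessment analysis. That scores are left out is an inference from the windows, the absence of a mapping rule and the no-imputation statement. The dummy tables attached to the SAP are not reproduced in the public file.

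Two stronger readings are tempting, and the documents support neither:

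- **A routine 3-month effectiveness assessment is lost.** The words "Every 3 months" in Protocol 7.3.1.2 belong to a recommended laboratory schedule for lymphocytes, neutrophils and hemoglobin. No section ties Mayo scoring or endoscopy to it.
- **One third of the effectiveness data is discarded.** The 35% is a share of days. It becomes a share of scores only under an even spread of visits, which sits badly with the named target weeks. Gap scores also keep the two un-windowed routes shown above.

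**Conclusion.** The point holds in a limited form. Two 25-day gaps follow exactly from the SAP's own figures, in a study without mandated visits. For remission, clinical response and mucosal healing, a score in a gap has no table to enter, including a closing score that the plan elsewhere says should be used.

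How many scores or patients are affected cannot be derived from the documents. The range of about 3% to 35% of scores rests entirely on assumed visit patterns. Upward bias in the time-point rates is possible rather than shown: it requires that patients whose closing scores fall in the gaps did worse than those tabulated. Protocol 7.2.5.1 lists lack of effectiveness among the reasons for stopping, which makes that plausible. The primary safety analysis is unaffected.

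**What to change.** In SAP 6.3:

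1. Add contiguous windows cut at the midpoints between targets, (56 + 112)/2 = 84 and (112 + 168)/2 = 140, for example days 29–84, 85–140 and 141–196. Within each, take the assessment nearest the target day. Show these results beside the ±15-day tables.
2. Report n at each time point and the number of scores outside every ±15-day window, so the loss is counted instead of assumed.
3. Add remission, clinical response and mucosal healing at the last assessment, to match the existing last-value Mayo analysis. The first item cannot replace this: under a nearest-to-target rule a day-60 score would displace a closing score on day 80.

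The cost is SAP wording and a mapping rule in the programs, with no new data. The downside is that some scores would lie up to 28 days from the nominal week: a day-84 score would be labelled week 8 and a day-85 score week 16. The last window would also run to day 196, beyond the 24-week collection point. Keeping the ±15-day tables alongside lets the reader judge this. If the analysis has already been run, the additions can be reported as labelled sensitivity tables. SAP 5.1 already provides for describing changes of method in the final report.

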7.2.5.1. Basic information

The following will be recorded on the CRF for each patient:

- Name of institution: Enter the name of the institution.
- Department: Enter the department name of the institution.
- Name of investigator: Enter the name of the contracted physician.
- Patient number: The investigator will sequentially assign each patient a patient identification number, which will be a 4-digit number. The total number of cases that need

to be collected will be allocated to each study site by Pfizer at the time of execution of a contract with each site.

- Completion of the study: If the patient completed 24 weeks of treatment (52 weeks for the long-term users), check “yes”. Otherwise, check “no” and choose reason for the discontinuation: AE; lack of effectiveness; others.
- Date of CRF completion: Record the date of CRF completion.
- Signature of investigator: Contracted investigator must sign after identifying the CRF.
- Confirmation of data privacy statement: If the patient has signed the data privacy statement to indicate agreement for using his/her personal and medical information, check the box of “yes” on the CRF. If not, check “no” and exclude the case from the study.

7.2.5.2. Demography and baseline characteristics

The following will be recorded on the CRF for each patient:

- Age: Record actual age of the patient at the time of enrollment. The age should be calculated by the date of birth.
- Sex: Check the box next to “male” or “female” on the CRF.
- Height: Record by unit of cm.
- Weight: Record by unit of kg.
- Herpes zoster vaccination: Record if the patient had received vaccine of herpes zoster: yes; no; unknown.
- Smoking: Record smoking status of the patient: ex-smoking; current smoking; non-smoking; unknown.
- Duration of the disease: Record the duration of disease since the date that the patient was initially diagnosed with UC.
- Severity of disease activity: Assess the severity (Mild, Moderate, Severe) by measuring Mayo or partial Mayo score and calculating the total score of 12 or 9 points based on clinical evaluation criteria: Stool frequency, rectal bleeding, findings of endoscopy, and physician's global assessment. Partial Mayo score excludes the findings of endoscopy. The severity for partial Mayo score is defined as 0-1 for remission, 2-4 for mild, 5-6 for moderate and 7-9 for severe disease activity.

- Previous UC treatments: Only record UC treatments received 6 months prior to the initiation of Xeljanz. Record name of the medication/therapy, route and duration of the administration, and overall response, if possible.
- Latent tuberculosis: Record if the patient has latent tuberculosis: yes; no; unknown.
- Renal impairment: Record if the patient has renal disorder: yes (severe/moderate/mild); none.
- Hepatic impairment: Record if the patient has hepatic disorder: yes (severe/moderate/mild); none.
- Other past/present diseases: Record “yes” or “no” for medical history. If “yes”, record adequate full name of the past or present disease according to the Medical Terminology Dictionary written by the Korean Medical Society. Past or present disease will be determined based on the date of the first dose of Xeljanz.

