7.3.3. Effectiveness evaluation

Effectiveness assessment will be performed by the accredited investigator in the Korean health care center. The investigator will perform the final effectiveness evaluation at baseline and after 8, 16 and 24 weeks of treatment based on the clinical impression and any of the commonly used effectiveness assessment criteria such as Mayo score or Partial Mayo score, and record the assessment results in each patient's CRF. 52nd week will be added for the long-term users. If the patient does not complete the 24 or 52 weeks of treatment, relevant data should be collected based on the last assessment performed at the time of treatment discontinuation. The final evaluation of the effectiveness will be determined by the investigator into 4 categories('Improved', 'Unchanged', 'Aggravated', 'Not assessable').

- Improved (Symptoms of ulcerative colitis have improved or showed adequate maintenance effect after taking Xeljanz)
- Unchanged (Symptoms have not changed much since taking Xeljanz)
- Aggravated (Symptoms have worsened after taking Xeljanz)
- Not assessible (Reason :)

If the overall effectiveness assessment is evaluated as 'Improved', 'Unchanged' or 'Aggravated', it is analyzed to be clinically significant. If the overall effectiveness assessment is evaluated as 'Not assessible', it is analyzed as not clinically significant. Among the 4 categories, 'Improved' is considered that the drug is effective. 'Unchanged' and 'Aggravate' are considered that there is a lack of effectiveness.

The Mayo score or the Partial Mayo score, which is referred in the effectiveness evaluation, are commonly used in actual medical practice. The Mayo score or the Partial Mayo Score at 8, 16 and 24 weeks(also 52 for the long-term users) will be assessed after the administration of Xeljanz, and Mayo Score measures the number of stool frequency, rectal bleeding, findings of endoscopy, and physician's global assessment. In total, based on the total score of 12 points, 0-2 points is rated as Remission, 3-5 as Mild, 6-10 as Moderate, and 11-12 as Severe. Partial Mayo Score is calculated by the sum of the remaining evaluations, except for the findings of endoscopy score. Based on the total score of 9 points, 0-1 is rated as Remission, 2-4 as Mild, 5-6 as Moderate and 7-9 as Severe.

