7.7.1. Safety analysis

The primary interest of this study is the incidence of AEs investigated during the re-examination period. Incidence of each AE will be presented with 95% confidence interval. Serious, related, and/or unexpected AEs will be summarized separately.

[figure not shown]
Safety analysis will be performed for all patients registered for this study who are prescribed at least 1 dose of Xeljanz according to the local label and followed up for safety data.

To identify the factors that affect safety, subgroup analysis for various factors will be performed, including the classification of AEs by body system, and comparison of incidence of AEs by sex, age, presence of concurrent diseases, presence of concomitant medications, baseline disease activity, etc.

In case the drug was administered to special populations such as elderly people over 65, or patients with renal or hepatic disorders during the study, subgroup analysis will also be performed for each of those populations. The safety and effectiveness of Xeljanz in pediatric patients have not been established.

Unexpected AEs/ADRs will be classified by medical review with reference to the local product document. Events already included in the “Precautions for use” section of the local product document will be classified as “expected”. All other events that are not included in the “Precautions for use” section of the local product document will be classified as “unexpected”. An unexpected AE includes any events that may be symptomatically and patho-physiologically related to an event listed in the labeling, but differs from the labeled event because of greater severity or specificity.

In the case of an adverse event with important potential risks and important identified risks in relation to the safety specification under the risk management plan, or if missing information patient group is recruited, actions according to the label will be taken, and the safety information is presented separately.

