#### **2.2. Study Design**

This is an open-label, non-comparative, non-interventional, prospective, and multi-center study conducted in Korean health care centers by accredited physicians (i.e., investigators). The study population will be adult patients with moderately to severely active UC who have had an inadequate response or intolerance to the basic treatments or biological agents. Clinical Severity of Ulcerative Colitis is classified as mild, moderate, or severe based on the Mayo score or partial Mayo score [Table 1].

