#### 6.1.1. Demographic and Baseline Characteristics

- 1) Sex will be presented in frequency and percentage.
- 2) Age (year) will be presented in n, mean, SD, median, minimum and maximum. Also, frequency and percentage of each group categorized according to the distribution for age will be presented.
- 3) Geriatric subjects ( $\geq 65$  years) will be presented in frequency and percentage.
- 4) Height (cm) will be presented in n, mean, SD, median, minimum and maximum.
- 5) Weight (kg) will be presented in n, mean, SD, median, minimum and maximum.
- 6) Disease duration\* (month) will be presented in n, mean, SD, median, minimum and maximum. Also, frequency and percentage of each group categorized according to the distribution for disease duration will be presented.

\*The duration from when ulcerative colitis was first diagnosed until the day that first dose of Xeljanz® is taken.

Disease duration (month) = (Year of disease duration  $\times$  12) + Month of disease duration

- 7) Disease severity will be presented in frequency and percentage.
- 8) Latent tuberculosis will be presented in frequency and percentage.
- 9) Herpes zoster vaccination will be presented in frequency and percentage.
- 10) Smoking will be presented in frequency and percentage.

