## **Statistical Analysis Plan for rPMS**

- Occurrence status of adverse events by their seriousness [SAE]
  - Results in death
  - Is life-threatening
  - Requires inpatient hospitalization or prolongation of hospitalization
  - Results in persistent or significant disability/incapacity
  - Results in congenital anomaly/birth defect
  - Other important medical event
- [Non-SAE]
- Occurrence status of adverse events by action taken
  - Permanently discontinued
  - Temporary discontinued or delayed
  - Dose reduced
  - Dose increased
  - No change
  - Not applicable
- Occurrence status of adverse events by their causality assessment to Xeljanz®
  - Related to Xeljanz®: ① Certain  
② Probable/likely  
③ Possible  
⑤ Conditional/unclassified  
⑥ Unassessable/unclassifiable  
⑦ Not applicable
  - Not related to Xeljanz®: ④ Unlikely
- Occurrence status of adverse events by their other causality assessment (In case of 'Unlikely')
  - Disease under the study
  - Other diseases
  - Concomitant treatment-medication or non-medication
  - Other

3) Occurrence status of adverse events by demographic and other baseline characteristics

- The incidence of adverse events and 95% C.I will be presented by categorical variables of demographic and other baseline characteristics.
- To identify statistically significant difference in the incidence of adverse events by categorical variables of demographic and other baseline characteristics, Chi-square test ( $\chi^2$  test) or Fisher's exact test (if the expected frequency for each cell under 5 is more than 20%) will be performed.

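### Baseline severity can be rated on full or partial Mayo, whose bands do not match, yet it is planned as a single factor for the adverse-event subgroup comparisons

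*Protocol*

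**What the plan says.** Protocol 7.2.5.2 asks the investigator to "Assess the severity (Mild, Moderate, Severe) by measuring Mayo or partial Mayo score and calculating the total score of 12 or 9 points". That section gives cut-offs for the partial score only ("The severity for partial Mayo score is defined as 0-1 for remission, 2-4 for mild", and so on upwards). The full-score bands appear in Protocol 7.3.3: "0-2 points is rated as Remission, 3-5 as Mild, 6-10 as Moderate, and 11-12 as Severe". The same section repeats the partial bands: "0-1 is rated as Remission, 2-4 as Mild, 5-6 as Moderate and 7-9 as Severe".

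SAP 2.2 keeps the choice of version open: "Clinical Severity of Ulcerative Colitis is classified as mild, moderate, or severe based on the Mayo score or partial Mayo score". It states no cut-offs and does not say which version takes precedence. SAP 6.1.1 item 7 then lists one variable: "Disease severity will be presented in frequency and percentage".

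On use, Protocol 7.7.1 plans "comparison of incidence of AEs by sex, age, presence of concurrent diseases, presence of concomitant medications, baseline disease activity, etc". SAP 6.2 item 3 applies chi-square or Fisher tests "To identify statistically significant difference in the incidence of adverse events by categorical variables of demographic and other baseline characteristics", and item 4 adds a logistic model. SAP 6.3 items 6 and 7 do the same for the effective rate, and SAP 6.4 repeats both sets in long-term users. The SAP items do not name severity. That it is included is the natural reading, because SAP 6.1.1 lists it among the baseline characteristics and Protocol 7.7.1 names disease activity.

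**The concern.** Separate cut-offs for two versions of a score are legitimate. The difficulty is that two non-equivalent sets of bands feed one variable. No visit or activity is mandated, and SAP 4.2 reports mucosal healing only where endoscopy was done, so the plan itself expects some patients without an endoscopy score. Two patients with identical stool, bleeding and global-assessment scores can then be labelled Moderate and Severe only because one was endoscoped.

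A comparison of adverse-event incidence between Moderate and Severe would partly compare patients with and without endoscopy. Whether or not a difference appears, it would be hard to interpret.

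A related question arises for remission and clinical response. SAP 4.2 items 3 and 4 give version-specific rules, while SAP 6.3 items 3 and 4 describe one achieved/not-achieved frequency per visit.

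**Working it through.** The plan states no figure on this point, so there is none to reproduce. The check enumerates subscore patterns using the documents' own cut-offs.

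**Inputs.** Four subscores, each 0 to 3 (Protocol Table 1). Partial total = stool + bleeding + global assessment. Full total = partial + endoscopy. Bands from Protocol 7.3.3. Remission and response rules from Protocol 7.3.3 and SAP 4.2; the partial response rule is taken from the protocol, because the SAP sentence drops a conjunction.

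**Step 1: labels for the same patient.**

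| Partial total | Partial label | Full label at endoscopy 0 / 1 / 2 / 3 | Combinations of the three subscores |
|---|---|---|---|
| 5 | Moderate | Mild / Moderate / Moderate / Moderate | 12 |
| 6 | Moderate | Moderate in all four | 10 |
| 7 | Severe | Moderate in all four | 6 |
| 8 | Severe | Moderate / Moderate / Moderate / Severe | 3 |
| 9 | Severe | Moderate / Moderate / Severe / Severe | 1 |

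For a partial score of 7, the full score runs from 7 + 0 = 7 to 7 + 3 = 10, always inside the 6–10 Moderate band.

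**Step 2: patterns that both scales call moderate or severe** (full ≥6 and partial ≥5).
- Both Moderate: 12×3 + 10×4 = 76
- Full Moderate, partial Severe: 6×4 + 3×3 + 1×2 = 35
- Both Severe: 3×1 + 1×2 = 5
- Total: 76 + 35 + 5 = 116; discordant 35/116 = 30.2%

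No pattern here is full Severe but partial Moderate, so the shift is one-way. Severe covers 5 of the 116 patterns on full Mayo and 35 + 5 = 40 on partial.

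**Step 3: restricted to endoscopy 2 or 3.** Both Moderate 12×2 + 10×2 = 44; discordant 6×2 + 3×1 = 15; both Severe 5. Discordant 15/64 = 23.4%, in the same direction.

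**Step 4: remission.** Stool 1, bleeding 0, global assessment 1, endoscopy 0 has a full total of 2 with no subscore above 1, so it meets the full rule. Its partial total is also 2, above the limit of 1, so it fails the partial rule. In the other direction, six patterns (all with endoscopy 2 or 3) meet only the partial rule if endoscopy is ignored. None do if a recorded endoscopy score counts among the other subscores that must not exceed 1.

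**Step 5: response.** The 150 baseline patterns with full Mayo ≥6, each paired with all 256 follow-up patterns, give 38,400 pairs. The 53 baselines have endoscopy 2–3, every subscore ≥1 and full Mayo ≥6, giving 53×256 = 13,568 pairs.

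| Baselines | Reading of the full-Mayo drop | Partial-only | Full-only | Discordant |
|---|---|---|---|---|
| 150 | strictly over 3 | 5,630 | 513 | 6,143 (16.0%) |
| 150 | at least 3 | 3,341 | 1,566 | 4,907 (12.8%) |
| 53 | strictly over 3 | 1,238 | 329 | 1,567 (11.5%) |
| 53 | at least 3 | 562 | 813 | 1,375 (10.1%) |

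In the 53 baselines, the excess changes sides with the reading.

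**The case against.** The best defence is that little depends on this factor. The primary summary, adverse-event incidence with its confidence interval, does not use severity. Severity is one of many exploratory factors in an uncontrolled surveillance study whose limits the protocol acknowledges. Protocol 7.3.3 does state both sets of bands. SAP 6.3 item 1 summarises both scores with their numbers of patients, so the mix of versions may be visible in the report. All of this stands and limits the weight of the point. It does not supply the missing rule on which version defines the subgroup.

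Pattern counts are also not patient rates. Among the 150 patterns with full Mayo 6–12, labels differ in 69, but 34 of those are Mild on the partial scale. Patients rated that way might not meet the indication and would not enter a Moderate-versus-Severe contrast. The 116-pattern set leaves them out for that reason. Size depends on the real score distribution; the one-way direction does not.

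A reader might infer that remission and response are certainly pooled, or that partial scoring inflates them. The documents support neither. Pooling is inferred from a single frequency per visit, and the dummy tables are not shown. The partial-only remission patterns depend on how one clause is read, and the direction of response discordance depends on another.

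**Conclusion.** The concern holds for the baseline-severity factor. Followed as written, the plan lets the Moderate/Severe label depend partly on whether endoscopy was scored, moving patients without it towards Severe. In unweighted patterns, 35 of 116 (30%) differ, or 15 of 64 (23%) when endoscopy is 2 or 3. The effect in patients cannot be sized, because neither the endoscopy share nor the score distribution is given. The conclusion assumes that both versions are in fact used and that severity is among the baseline characteristics tested.

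It would go too far to say that the study's safety result or effective rate is biased. Overall adverse-event incidence does not use severity, and the effective rate rests on the investigator's category. What is harmed is the interpretation of the severity subgroup tests and models.

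For remission and response, the two rules can disagree, which is reason enough to report by version. No direction of bias is established.

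**What to change.** This is a cheap improvement.

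1. State in the SAP that the baseline-severity factor is derived on partial Mayo, using the protocol's partial bands, for every patient with the three subscores, whichever version was recorded. Give the full-Mayo label in endoscoped patients as a sensitivity table.
2. Unless the dummy tables already do so, show remission and response in separate rows by version, each with its own denominator.
3. Say whether a recorded endoscopy score counts among the other subscores for partial-Mayo remission, and whether the full-Mayo response threshold means strictly more than 3 points or at least 3.

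The cost is a few SAP sentences, some derivation code, one extra table and a few rows. No new data should be needed, since SAP 6.3 item 1 already summarises each subscore at baseline. The downside is that the main factor ignores endoscopy where it exists, and some patients who are Moderate on full Mayo will fall in the partial Mild band, so the table needs a Mild row.
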